6.2.2 FORMULATION, APPEARANCE, PACKAGING, AND LABELING

Study Drug: IXT-m200 is formulated as a solution containing approximately 20 mg/mL IXT-m200 in 10 mM sodium phosphate, pH 6.5, 150 mM sodium chloride, and 0.05% w/v polysorbate 80. The product is

a clear solution packaged in glass vials with stoppers and flip-off seals. Catalent Pharma Solutions manufactures the formulated active pharmaceutical ingredient.

Labels will be similar to the following:

InterveXion Therapeutics®
Anti-methamphetamine IXT-m200
18.5-21.5 mg/mL
Manufactured: DD MMM YYYY
DP Lot: XXXXXX
Catalent Lot: XXXXX
10 mM sodium phosphate, 150 mM sodium chloride, pH 6.5, with 0.05% Tween 80
Store refrigerated at 2 to 8°C
CAUTION: New Drug – Limited by Federal (or United States) law to investigational use only.
InterveXion Therapeutics, LLC
[name]

Placebo: Normal saline (0.9% sodium chloride) should be a clear solution for injection. Packaging and labeling will be appropriate for use.

Only unblinded study staff will have access to the labeled study drugs.

6.2.3 PRODUCT STORAGE AND STABILITY

IXT-m200 vials are single-use and should be stored refrigerated at 2 to 8°C. The stability of the product is still under investigation and stability protocols will run concurrent to the study. A previous lot of IXT-m200 remained stable after 48 months of refrigerated storage when the stability protocol was terminated.

6.2.4 PREPARATION

An unblinded staff member (e.g., pharmacist) will prepare the study drugs for administration. The appropriate amount of IXT-m200 should be administered over 30 min. Since IXT-m200 is a clear solution, it will appear similar to saline placebo.

Placebo: Normal saline requires no preparation prior to administration.

6.3 MEASURES TO MINIMIZE BIAS: RANDOMIZATION AND BLINDING

Each potential participant will be assigned a unique number in the screening process (screening number). This number will be used to identify the participant throughout the study.

Participants who qualify will be randomized on Day 1 to 3 g IXT-m200 or placebo (7:2).

Unblinding of treatment assignment during the study is discouraged and should occur only if it is absolutely necessary for the Investigator, Sponsor, or participant to know what he or she received for safety reasons. If the Sponsor or the Investigator deems identification of the study drug to the participant as necessary for the purpose of providing urgent care, the pharmacy will inform the Investigator of the assignment, who will notify the Sponsor and participant. The process of unblinding will be appropriately documented in the Investigator file. The date and reason for the unblinding must be recorded. When

possible, the Sponsor should be notified prior to unblinding; otherwise, they must be notified within 24 hours after unblinding.

6.4 STUDY INTERVENTION COMPLIANCE

Study drug is administered by intravenous infusion by qualified personnel who are blinded to the treatment assignment of the participant. Compliance with dosing will be verified by reference to the CRF documentation of dosing.

6.5 CONCOMITANT THERAPY

All concomitant medications (i.e., prescription medications, over-the-counter medications, non-prescription medications, and supplements) taken during study participation will be recorded on the CRF. For this protocol, a prescription medication is defined as a medication that can be prescribed only by a properly authorized/licensed clinician.

7 STUDY INTERVENTION DISCONTINUATION AND PARTICIPANT DISCONTINUATION/WITHDRAWAL

7.1 DISCONTINUATION OF STUDY INTERVENTION

The criteria outlined in section 8.2.3.1 will be used to categorize the severity of all AEs. The Sponsor, in consultation with the Investigator, will suspend enrollment until a full safety review is performed if any 1 of the following events occurs, unless the event was clearly unrelated to study drug administration:

- Two (2) participants experience a Grade 3 AE; or,
- One (1) participant experiences a Grade 4 AE; or,
- A death occurs.

Events unrelated to study drug administration include those that are temporally unrelated to study drug administration, such as events occurring prior to dosing; or events in which the participant is a passive victim, such as a passenger in a motor vehicle crash.

A decision to reinitiate enrollment will be made by the Sponsor following any necessary consultation with the appropriate authorities based on the results of the safety review. All other study procedures will continue per protocol during any study pause.

7.2 PARTICIPANT DISCONTINUATION/WITHDRAWAL FROM THE STUDY

Participants who withdraw consent for future study visits (following early termination assessments) will be considered ‘withdrawn’. Participants are free to withdraw at any time upon request; they will be asked to complete early termination assessments as soon as possible.

Participants that receive less than the complete single dose of study drug but agree to continue participation in other study procedures and assessments will be considered ‘discontinued’. Participants are free to discontinue at any time during dosing upon request. Participants will be encouraged to complete study visits and assessments, even if they elect to discontinue study drug administration. In this case, all study activities will be completed per protocol with the exception of dose administration.

The Investigator may discontinue a participant from study drug administration for the following reasons:

- the participant meets an exclusion criterion (either newly developed or not previously recognized) that precludes further study participation, such as an infusion reaction,
- any clinical AE, laboratory abnormality, or other medical condition or situation occurs such that continued participation in the study would not be in the best interest of the participant,
- significant non-compliance by the participant,
- if, in the Investigator's opinion, continuation with study drug administration would be detrimental to the participant's well-being,
- at the specific request of InterveXion (Sponsor) or the Investigator.

In all cases, the reason for withdrawal or discontinuation must be recorded in the CRF and in the participant's medical records. If the reason is not known, an attempt must be made to follow up with the participant to establish whether the reason was an AE, and, if so, this AE must be reported. Once the participant has been contacted and expresses their decision to withdraw from further participation in the study, the research staff will cease to try to make further contact.

Participants who withdraw or are discontinued may be replaced at Sponsors discretion until there are 6 participants who have completed the protocol through Day 63.

7.3 LOST TO FOLLOW-UP

A participant will be considered lost to follow-up if he or she fails to return for the final scheduled visit, including an early term visit, and is unable to be contacted by the study site staff.

The following actions must be taken if a participant fails to return to the clinic for a required study visit:

- The site will attempt to contact the participant and reschedule the missed visit, counsel the participant on the importance of maintaining the assigned visit schedule, and ascertain if the participant wishes to and/or should continue in the study.
- Before a participant is deemed lost to follow-up, the Investigator or designee will make every effort to regain contact with the participant (where possible, 3 telephone calls and, if necessary, a certified letter to the participant's last known mailing address or local equivalent methods). These contact attempts should be documented in the participant's medical record or study file.
- Should the participant continue to be unreachable, he or she will be considered to have withdrawn from the study with a primary reason of lost to follow-up.

8 STUDY ASSESSMENTS AND PROCEDURES

8.1 SAFETY AND OTHER ASSESSMENTS

Assessments are to be performed at the time points described in the Schedule of Activities (1.3).

8.1.1 ELIGIBILITY CRITERIA

- Diagnostic and Statistical Manual of Mental Disorders, 5th Edition (DSM-5) criteria checklist should be used to assess participants for Substance Use Disorders (including METH, opioids, alcohol, nicotine, marijuana, etc.)

- Urine drug screen to include illicit substances (barbiturates, benzodiazepines, cocaine, opiates, phencyclidine, MDMA, METH, or amphetamine) on Day 1 (a positive test for tetrahydrocannabinol may be acceptable if the subject is not intoxicated at the discretion of the Investigator).

8.1.2 MEDICAL AND MEDICATION HISTORY

- A complete medical history will be obtained by interview and any available medical records at screening. Interim medical history will be obtained at all subsequent time points.
- A complete medication history will be obtained by interview and any available medical records at screening, with particular attention to any medications taken in the previous 12 months. The medication history, including concomitant medications, will be updated at all subsequent visits.

8.1.3 VITAL SIGNS

- Vital sign measurements (heart rate, blood pressures [systolic and diastolic], respiratory rate, temperature [oral], and pulse oximetry readings) will be obtained after the participant has been resting for at least 5 minutes.

8.1.4 PHYSICAL EXAM

- Physical examination (excluding rectal/genital and breast examination) will consist of an examination of the following: general appearance, neurological, skin, head, eyes, ears, nose, throat, neck, lymph nodes, chest, heart, abdomen, and extremities.
- Targeted physical exams will include heart, lungs, abdomen, skin, and site of injection. Additional areas may be targeted if AEs or other complaints require appropriate and more detailed exams.
- Height and weight will be recorded at screening; weight will be recorded at subsequent visits.

8.1.5 PSYCHIATRIC EVALUATION

- A psychiatric history will be obtained at screening evaluating for (but not limited to) the following: major current depression, psychosis, bipolar illness, organic brain disorder, anorexia nervosa or bulimia disorder or dementia, which require ongoing medication or which would make study compliance difficult in the opinion of the Investigator.

8.1.6 PREGNANCY TEST

- Urine pregnancy tests will be performed on all females at designated visits.

8.1.7 LABORATORY TESTS

The below laboratory tests will be centrally assessed:

- Hematology
 - Erythrocytes: red blood cell (RBC) count, hematocrit, hemoglobin, mean corpuscular hemoglobin, mean corpuscular hemoglobin concentration, mean corpuscular volume, red cell distribution width, and reticulocyte count as an absolute value.
 - Leukocytes: WBC and differential (basophils, eosinophils, lymphocytes, monocytes, and neutrophils) reported as absolute values.

- Coagulation: platelet count, prothrombin time measured as international normalized ratio, activated partial thromboplastin time.
- Serum Chemistry
 - Liver: alkaline phosphatase, ALT, AST (serum glutamic-oxaloacetic transaminase), bilirubin (total, direct, and indirect), gamma-glutamyl transferase, and lactic dehydrogenase.
 - Renal: blood urea nitrogen, creatinine, and uric acid.
 - Electrolytes, sodium, potassium, chloride, and carbon dioxide.
 - General: CPK, albumin, calcium, magnesium, glucose (fasting), phosphate, protein (total), amylase, and lipase.
- Urinalysis
 - Microscopic: pH, specific gravity, glucose, ketones, leukocyte esterase, nitrites, occult blood, and protein, RBCs/hpf, WBCs/hpf, bacteria, casts, epithelial cells, mucous threads, and crystals.
 - Quantitative: protein and creatinine if microscopic is positive for protein.

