1.2 SCHEMA

1.3 SCHEDULE OF ACTIVITIES

Assessment ^a	Screening	Inpatient		Follow-up (± 1 day)	Follow-up (± 3 days)		ET
Study Week	≤ -1	1		2	3-17	18	NA
Study Day	-30 to -1	1 ^b	2	8	15, 22, 29, 36, 43, 64, 85, 106	127	NA
Informed consent	X						
Initial evaluations							
Eligibility criteria							
Demographics							
Medical history and medications		X					
Vital signs ^c							
Physical exam							
Psychiatric evaluation							
Urine pregnancy test							
Laboratory tests ^d	X	X	X	X	X (29 and 64 only)		X
Urine drug screen		X					
Wellness check							
Update medical history		X	X	X	X	X	X
Update medications							
Vital signs ^c							
Targeted physical exam							
ECG ^e	X						
Urine pregnancy test	X					X	X
Blood for cytokines ^f	X						
Blood for PK ^g	X	X		X	X	X	X
Blood for HACA ^h	X					X	X
Randomization	X						
Dose administration ⁱ	X						
AE monitoring				Continuous			X

Abbreviations: ECG – electrocardiogram; ET – early termination visit; HACA – human anti-chimeric antibodies; NA – not applicable; PK – pharmacokinetic

^a Descriptions of assessments are in Section 8.1.

^b Study Day -1 is the day prior to the first dose. Study Day 1 is the day of the first dose.

^c Vital sign measurements will be taken on Day 1 starting with a pre-dose measurement (≤ 30 min prior), then 0.25, 0.5, 1, 2, and 4 hours (± 5 min) after dosing starts, and as needed afterward until normalization. Measurements will be obtained once on each non-dosing day. Each test may be repeated once at each time point if the initial result is out of range.

^d Laboratory tests require blood and urine sampling for hematology, serum chemistry, and urinalysis. Samples are to be taken at screening, pre-dose and 2-hr post-dose completion (± 10 min) on Day 1, and once on Days 2, 8, 29, and 64.

^e ECGs are to be done pre-dose (up to 2 hr prior) and 30-min post-dose completion (± 15 min) on Day 1.

^f Cytokine samples are to be taken pre-dose (≤ 60 min prior) on Day 1. If a participant has an infusion reaction, cytokine sampling at 1- and 4-hours post-dose (± 10 min) should be performed. If no infusion reaction is observed, pre-dose samples will not be analyzed.

^g PK samples are to be taken pre-dose (≤ 30 min prior), then 1, 4, and 8 hr (± 10 min) and 24 hr (± 30 min) after the start of the infusion on Day 1. All other PK samples are to be collected once each visit.

^h HACA samples are to be taken pre-dose (≤ 60 min prior) on Day 1 and once on Day 126.

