6.1.2 DOSING AND ADMINISTRATION

Participants will only be randomized and dosed with study drug if they have passed all screening requirements before or on Day 1. Participants will be randomized on Day 1 to receive 3 g IXT-m200 or placebo (7:2). Each participant will receive 1 dose of assigned study drug on Day 1.

Participants should lie supine or semi-reclined during dose administration. Each dose will be given with an infusion pump over 30 minutes with a 50-mL saline flush dispensed after each dose to ensure the entire dose is flushed through the infusion set. The study drug infusion start/stop time, infusion rate, infusion volume, whether the infusion was completed, if it was stopped, or stopped and restarted will be recorded.

Participants will be asked to eat a light meal prior to arriving at the study center but not have anything but clear liquids to eat or drink for 1 hour before appointment time. Participants will be offered a light meal after dosing completion.

All study drug doses will be administered in a blinded manner by the Investigator or designee.

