### **6.3 Safety Population: All participants who receive exposure to study drug, including placebo comprise the Safety Population. This population will be used for all demographic and safety summaries. Safety Analyses**

Safety analyses will be presented by IXT-m200 and placebo groups and for all participants in the safety population.

Treatment-emergent adverse events (TEAEs) and serious TEAEs will be summarized by SOC and preferred term, and by severity (Grades 1, 2, 3, or 4) and relationship to treatment for IXT-m200 and placebo groups. The analysis of TEAEs by severity will count TEAEs by worst severity if an individual participant has a TEAE with more than one severity. The analysis of TEAEs by relationship to treatment will define treatment-related TEAEs as including all TEAEs assessed as definitely, probably, or possibly related to treatment, and non-treatment-related TEAEs as including all TEAEs assessed as unlikely and unrelated to treatment.

Vital signs, physical exam, pregnancy test, laboratory tests, and ECG will be tabulated. Descriptive statistics will be used to summarize continuous variables and change from baseline, which is defined as the most recent observation before dosing. Frequency and shift tables will be created for categorical variables.

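### Glucose is specified as fasting, but the dosing-day meal instruction makes the Day 1 pre-dose baseline probably non-fasting, so its change from baseline may be confounded with meal state

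*Protocol*

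**What the plan says.** - **Specification.** Protocol 8.1.7 lists "glucose (fasting" among the general serum chemistry tests. It gives no fasting duration and makes no exception for any visit.
- **Meal before dosing.** Protocol 6.1.2: "Participants will be asked to eat a light meal prior to arriving at the study center". The only restriction is to "clear liquids to eat or drink for 1 hour before appointment time".
- **Meal after dosing.** Same section: "Participants will be offered a light meal after dosing completion".
- **Sampling.** Protocol 1.3, footnote d: "Samples are to be taken at screening, pre-dose and 2-hr post-dose completion (± 10 min) on Day 1". Later draws, one per visit, fall on Days 2, 8, 29 and 64. The schedule also marks laboratory tests at early termination. No window is stated for the pre-dose sample.
- **Baseline.** SAP 6.3 summarises change from baseline, "which is defined as the most recent observation before dosing". The same section plans shift tables for categorical variables and presents safety results by arm and for all participants together.

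Neither document defines fasting, gives a meal instruction for the other laboratory visits, or says how a non-fasting glucose value is to be labelled or analysed.

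**The concern.** A site that follows 6.1.2 to the letter would normally draw a non-fasting sample for an analyte that 8.1.7 calls fasting. The SAP then makes that sample the reference for every later glucose comparison. If the later samples are fasting, change from baseline compares two metabolic states and can show a movement with no drug effect behind it. If glucose is classed as low, normal or high for a shift table, a non-fasting value read against a fasting range can also be put in the wrong baseline category.

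Safety is the primary objective, and fasting status cannot be reliably recovered later if it is not recorded at the draw.

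**Working it through.** The plan states no figure on this point. The sample size is empirical and no hypothesis is tested, so there is nothing to reproduce. The check is a timeline and a small decomposition.

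**Timeline on Day 1** (Protocol 1.3 and 6.1.2)

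1. Pre-dose sample: the guaranteed food-free interval is 1 h plus the time from appointment to draw, which is not stated. It may be longer, because no earliest time is set for the meal.
2. Post-dose sample: 2 h ± 10 min after dose completion, so 1 h 50 min to 2 h 10 min after the infusion ends. With a 30-min infusion, that is 2 h 20 min to 2 h 40 min after it starts.
3. A post-dose meal eaten before that draw would be at most about 2 h 10 min old. Whether it is eaten before or after the draw is not fixed.

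**Which sample is baseline.** Under SAP 6.3 it is the Day 1 pre-dose sample when present. Screening (Day -30 to -1) serves only if that sample is missing. The meal offered after dosing cannot affect baseline.

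**Effect on the tables.** Let F be a participant's fasting glucose and d the drug effect at a visit (zero on placebo). Let m be the meal effect in the baseline sample and v the meal effect in the later sample. The documents give neither m nor v.

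- Change = (F + d + v) − (F + m) = d + (v − m).
- Later sample fasting, as 8.1.7 requires: v = 0, so change = d − m.
- Later sample in a similar non-fasting state: v ≈ m, so change ≈ d.
- 2-hour sample on Day 1: change = d + (v − m). The sign of the meal term is unknown, since it depends on whether and when the second meal is eaten.
- All participants combined, with 7 active and 2 placebo: mean change = (7/9)d + (v − m) = 0.78d + (v − m). The drug effect is diluted and the meal term remains in full.
- Active minus placebo: [d + (v − m)] − [0 + (v − m)] = d in expectation, because both arms get the same meal instructions.

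**Precision of that contrast.** With a common SD of the change, SE = SD × √(1/7 + 1/2) = SD × √0.643 = 0.80 SD.

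**The case against.** The strongest reply is that little follows from the conflict between 8.1.7 and 6.1.2. Several stronger readings are tempting, and the documents do not support them.

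- **That the baseline is certainly a fed value.** Participants are asked to eat, not required to. No earliest meal time is set, and the time from appointment to draw is not given. Probably non-fasting is as far as the text goes.
- **That the 2-hour sample follows a meal.** The second meal is only offered, with no time fixed against the draw.
- **That glucose change is purely a product of meals, or is shifted by a known amount.** The shift d − m needs fasting later samples. Apart from the label in 8.1.7, nothing instructs fasting on Days 2, 8, 29 or 64. If those samples are also non-fasting, the shift may largely vanish. No figure for m is available from the documents.
- **That the comparison with placebo is biased.** It is not, in expectation, in a randomised, blinded design with common meal instructions. Two placebo participants limit precision for every analyte, not only glucose.
- **That the primary count is contaminated.** A high pre-dose value precedes treatment, and a raised baseline pushes later changes downward. Only the 2-hour sample could be raised by the second meal, and only if the meal came first. The value would still have to be reported as an adverse event and judged at least possibly related. If that happened in one active participant, it would be 1/7 = 14% of the arm, but nothing makes it automatic.

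The CRF is not among the documents, and the SAP keeps its table shells in a separate file. Meal time may therefore already be collected.

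All of these limits stand. What survives them is that the two protocol sections cannot both be followed in the ordinary case, and that the SAP places the affected sample at baseline.

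**Conclusion.** The point holds in limited form. The fasting specification in 8.1.7 conflicts with the dosing-day meal instruction in 6.1.2. Under SAP 6.3, the sample most directly affected is the glucose baseline. Within-arm and all-participant change from baseline, and any glucose shift table, may be confounded with meal state. The amount is m if later samples are fasting and near zero if they are in a similar non-fasting state; the documents settle neither. The between-arm difference is not systematically biased but is imprecise (SE 0.80 SD at 7 versus 2, assuming a common SD and the planned allocation).

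The scope is one analyte in descriptive safety tables. No hypothesis test or sample size is affected, and an effect on the primary endpoint is conditional. This is a minor point, worth correcting because the correction is cheap and the information is hard to recover later.

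**What to change.** 1. Reconcile Protocol 8.1.7 with 6.1.2. Which meal or fasting rule applies on the dosing day is the sponsor's decision; the two sections need to agree.
2. Record time of last meal, or fasting status, with each chemistry sample, unless the CRF already does so.
3. Read each glucose value against the reference range for its actual fasting status.
4. Add to SAP 6.3 that glucose change from baseline and shift compare samples in the same fasting state, and are flagged as non-comparable where no matching sample before dosing exists.

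The cost is one CRF field and one SAP sentence. The drawback is that the matching sample may be the screening one, up to 30 days before dosing, so glucose could have an older baseline than the other analytes. With 9 participants, a footnote to the table can show this.
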